9.0 Study Withdrawal/Discontinuation

A study subject will be discontinued from participation in the study if any of the following occur:

- Unacceptable toxicity or serious adverse event
- Intercurrent illness, or other medical condition or situation occurs such that continued
 participation in the study would not be in the best interest of the subject in the opinion of the
 treating investigator
- Development of any exclusion criteria
- Subject withdrawals consent to continue in the research for any reason
- Vaginal bleeding of postmenopausal women on treatment cream

Handling of Withdrawals

Subjects who are agreeable may either undergo an exam and exit interview or complete the study procedures as previously described and completed in Study Visit 1 at the time of withdrawal from the study.

If a subject withdraws, a replacement subject may be recruited.

10. Statistical Considerations

This study will be a placebo-controlled, single center study with 3 arms of women planning on undergoing surgery for pelvic organ prolapse.

The primary outcome will be vaginal epithelial thickness based on OCT measures. Findings of collagen and elastin scores, epithelial/stromal/muscularis thickness, cytokines, MMPs, inflammatory cells, and receptors will be also compared between groups. Appropriate statistical analysis for ordinal (e.g. scores) and continuous (e.g. thickness) data will be applied, including tests to determine normality (Shapiro-Wilk) and analysis with ANOVA if criteria are met (e.g. normal, continuous). If ANOVA criteria are not met, then Kruskal-Wallis will be performed for non-normal, ordinal (e.g. scores) data sets.

Power Analysis

Preliminary and historical data are available for OCT thickness, therefore power analysis was based on differences in the OCT thickness mean difference between groups of 40 micrometers with standard deviation 18, and 80% power. Based on T-test and Bonferonni correction (alpha/number of tests = 0.025) for 2 comparisons (1. postmenopausal treatment vs placebo and 2. reproductive age women at 2 different stages of the cycle), five subjects were calculated to be needed per arm to be able to reject

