the null hypothesis that the population means of the groups are equal. For example, the postmenopausal group with no estrogen is expected to have epithelial thickness of 100um, the postmenopausal group that receives estrogen is expected to have epithelial thickness of 180um, and the reproductive age women are expected to have epithelial thickness of 240um at follicular phase and 200um at the luteal phase.

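### Read as a two-sided comparison between groups, five women per arm gives about 76% power at 40 µm rather than the stated 80%, and one power statement covers two comparisons that need separate ones

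*Combined protocol and SAP*

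**What the plan says.** Section 10 sets the endpoint: "The primary outcome will be vaginal epithelial thickness based on OCT measures". The Power Analysis in that section states that "power analysis was based on differences in the OCT thickness mean difference between groups of 40 micrometers with standard deviation 18, and 80% power". It uses a t-test with a "Bonferonni correction (alpha/number of tests = 0.025) for 2 comparisons": estrogen against placebo in postmenopausal women, and two cycle stages in reproductive-age women. From this, "five subjects were calculated to be needed per arm to be able to reject" the null hypothesis that the group means are equal.

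The same paragraph then gives expected thicknesses. Untreated postmenopausal women are put at 100 µm, and "the postmenopausal group that receives estrogen is expected to have epithelial thickness of 180um". Reproductive-age women are put at 240 µm in the follicular phase and 200 µm in the luteal phase.

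Section 5.0 schedules the second visit of each premenopausal woman in the opposite cycle phase from her first. Section 3.0 sets the completer target at 15 or more, with at least 10 postmenopausal and 5 reproductive-age women, out of up to 30 enrolled.

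The text does not say whether the tests are one- or two-sided, whether 18 µm is the SD between women or the SD of within-woman differences, or whether the cycle-phase test is paired.

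**The concern.** One set of inputs and one answer are offered for two comparisons of different structure. Estrogen versus placebo compares independent arms. Cycle phase compares two measurements in the same woman. The single difference used, 40 µm, matches the expected means of only the second, while the wording of the calculation (between groups, per arm) describes the first.

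On the usual two-sided two-sample reading, the stated power is also not reached with five per arm. This paragraph is the only justification for the 15-completer target. Without the missing details a reader cannot tell what the study can detect in either comparison, and in particular cannot judge how informative a null cycle-phase result would be.

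**Working it through.** **Inputs (all from section 10 unless noted).** Difference 40 µm; SD 18 µm; level 0.025 per comparison; n = 5 per arm; expected means 100 and 180 µm (placebo, estrogen) and 240 and 200 µm (follicular, luteal). Same-woman measurement of cycle phase is from section 5.0. The within-woman correlation is not in the documents, so it is varied below as an assumption.

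**Formulas.** Power comes from the noncentral t distribution.
- Two-sample: df = 2n − 2, noncentrality = (difference/SD) × √(n/2).
- Paired: df = n − 1, noncentrality = (difference/SD of differences) × √n. If 18 µm is the SD at each phase and ρ the within-woman correlation, the SD of differences is 18 × √(2(1 − ρ)).

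**Step 1. Can the plan's five be reproduced?** Yes, at level 0.025, in two ways:
- One-sided two-sample t-test: n = 4 gives 74.5%, n = 5 gives 86.7%.
- Two-sided paired t-test with SD of differences 18: n = 4 gives 63.9%, n = 5 gives 85.9%.

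**Step 2. Two-sided two-sample t-test at 0.025.** Here 40/18 = 2.222, and 2.222 × √2.5 = 3.514 on 8 df, with critical value 2.752.

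| n per arm | Power at 40 µm |
|---|---|
| 4 | 59.5% |
| 5 | 76.0% |
| 6 | 86.6% |

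With five per arm, 80% power requires a difference of 41.9 µm, or an SD of at most 17.2 µm. At two-sided 0.05, without the correction, five would suffice (86.7%; four gives 74.5%).

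**Step 3. Which comparison does 40 µm fit?** Estrogen versus placebo: 180 − 100 = 80 µm. Cycle phase: 240 − 200 = 40 µm. Only the second matches.

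**Step 4. Estrogen versus placebo at the expected 80 µm.** 80/18 = 4.444, and 4.444 × √2.5 = 7.027 on 8 df. Power with five per arm, two-sided 0.025, is 99.98%.

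**Step 5. Cycle phase as a paired t-test.** Five women, 4 df, two-sided 0.025, 40 µm. If 18 µm is the SD of differences, power is 85.9%. If 18 µm is the SD at each phase:

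| Assumed ρ | SD of differences (µm) | Power |
|---|---|---|
| 0 | 25.5 | 57% |
| 0.3 | 21.3 | 73% |
| 0.5 | 18.0 | 86% |
| 0.7 | 13.9 | 97% |

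Reaching 80% needs ρ of about 0.41.

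**The case against.** The strongest reply is that five is a correct answer to a calculation the text allows. Sidedness is not stated, and a one-sided test at 0.025 gives five. So does a two-sided paired test if 18 µm is the SD of differences. That stands: the 76% must be presented as conditional on a two-sided two-sample test. It does not settle the matter. The null of equal means and the planned ANOVA or Kruskal-Wallis tests are non-directional, and the paired reading cannot be carried over to two randomised arms. No single two-sided t-test reading gives five for both named comparisons. A normal approximation would put five per arm at 89.8% two-sided, but the plan specifies a t-test and the approximation is poor at 8 df.

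It can also be said that sizing on the smaller expected difference is cautious, and that five is a floor. Both are true. The 40 µm is half the expected treatment effect. Section 3.0 allows up to 30 women, and section 9.0 lets withdrawals be replaced, so six per arm lies within planned enrolment.

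Four stronger conclusions are tempting and should not be drawn:
- *The trial is underpowered.* The randomised comparison has over 99.9% power at the plan's own expected means and SD.
- *The power statement describes neither comparison.* The 40 µm is exactly the expected cycle-phase difference, and it is conservative for treatment.
- *The Bonferroni correction was left out.* Five is what the uncorrected two-sided two-sample test gives, but in the paired calculation with SD of differences 18 the correction moves n from 4 (82.9% at 0.05) to 5. The documents do not show which calculation was run.
- *Cycle-phase power is below 60%.* That requires 18 µm to be the SD at each phase and essentially no correlation between two measurements in the same woman.

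**Conclusion.** The point holds in conditional form. As a two-sided two-sample t-test at 0.025 with SD 18 µm, five per arm gives 76.0% power at 40 µm, about 4 points short of the stated 80% and one woman per arm short of the number needed. The 40 µm belongs to the cycle-phase comparison, which is paired. Its power with five women is 86% if 18 µm is the SD of differences. Otherwise it runs from 57% to 97% over assumed correlations of 0 to 0.7.

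The defect is an incompletely specified calculation that does not correctly describe both comparisons. It is of minor to moderate weight, because the expected treatment difference is well covered. These figures take the plan's SD and expected means as given, and assume normal data and equal SDs.

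**What to change.** Rewrite the Power Analysis by comparison. State that tests are two-sided at 0.025, and say what the 18 µm SD refers to.

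1. **Estrogen versus placebo**, two-sample t-test, five per arm, SD 18 µm: power above 99.9% at the expected 80 µm and 76% at 40 µm; difference detectable with 80% power about 42 µm.
2. **Cycle phase**, paired t-test in five women, 40 µm: give the assumed SD of the within-woman difference and its source. If it is 18 µm, power is 86%. If 18 µm is the SD at each phase, report 57%, 73%, 86% and 97% for assumed correlations of 0, 0.3, 0.5 and 0.7, and note that 80% needs about 0.41.

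Remove the single claim that five per arm gives 80% power at 40 µm for both comparisons, and explain how 40 µm relates to the expected 80 µm treatment difference.

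The cost is protocol wording, plus a look at the preliminary OCT data to establish which SD the 18 µm is. No extra patients, visits or procedures are needed.

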5.0 Study Procedures

Postmenopausal Women

Study Visit 1

Within approximately 30 days of the scheduled surgery date, the postmenopausal subjects will come to the Pelvic Health Clinic at Victory Lakes to have an optical coherence tomography (OCT) scan and pelvic floor (endovaginal) ultrasound.

Both of these tests involve a vaginal probe being inserted in the vagina to collect pelvic organ and tissue images. The OCT produces higher resolution 3-dimensional images and takes 10-15 minutes or less and the endovaginal ultrasound takes about 30-45 minutes.

At this visit, up to 20ml of blood may be drawn for serum hormone levels of estradiol and testosterone, DHEA and androstendione.

Subjects will complete Uro Gyn Clinical Intake Form if not previously within 3 months. The Intake Form includes the following questionnaires: UDI-6, POPDI-6, CRADI-8, PFIQ, PISQ-12 (see protocol appendix for questionnaries).

Subjects will be randomized to placebo or estrogen vaginal cream.

Subjects will be provided with a topical vaginal cream to use daily until 2 days prior to your scheduled surgery date (4-6 weeks). Subjects will apply 0.5 gram of the study vaginal cream daily. Subjects will be given a study diary as a reminder and to record usage and will return their spent tube of cream for weighing as a measure of compliance.

Study Visit 2

Subject will return within a week prior to schedule surgery. Subjects will repeat the OCT, pelvic floor ultrasound and the questionnaires as done in Study Visit 1. Up to 20ml of blood may be drawn to repeat serum hormone levels of estradiol and testosterone, DHEA and androstendione.

Premenopausal Women

Study Visit 1

Premenopausal subjects will have their studies visits 1 scheduled in order to coincide with the subject's follicular or luteal phase of their menstrual cycle. Study visit 2 will be scheduled in order to coincide with opposite phase from study 1.

Premenopausal subjects will come to the Pelvic Health Clinic at Victory Lakes to have an optical coherence tomography (OCT) scan and pelvic floor (endovaginal) ultrasound.

Both of these tests involve a vaginal probe being inserted in the vagina to collect pelvic organ and tissue images. The OCT produces higher resolution 3-dimensional images and takes 10 minutes or less and the endovaginal ultrasound takes about 30 minutes.

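### Section 10 splits alpha by single-step Bonferroni for the two OCT comparisons; Holm keeps the same 5% familywise error and adds 0 to 18 points of cycle-phase power, depending on an unstated within-woman correlation

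*Combined protocol and SAP*

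**What the plan says.** Section 10 (Power Analysis) sizes the trial on "differences in the OCT thickness mean difference between groups of 40 micrometers with standard deviation 18, and 80% power". The error rule is given in the same place: "Based on T-test and Bonferonni correction (alpha/number of tests = 0.025) for 2 comparisons". The two comparisons are "1. postmenopausal treatment vs placebo and 2. reproductive age women at 2 different stages of the cycle", and the result is that "five subjects were calculated to be needed per arm to be able to reject" the null hypothesis.

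The example means that follow are not all 40 um apart. For placebo, "the postmenopausal group with no estrogen is expected to have epithelial thickness of 100um"; for active treatment, "the postmenopausal group that receives estrogen is expected to have epithelial thickness of 180um". That is a difference of 80 um. For reproductive-age women the plan expects "epithelial thickness of 240um at follicular phase and 200um at the luteal phase", a difference of 40 um.

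The paragraph of Section 10 that describes the analysis names ANOVA or Kruskal-Wallis and gives no multiplicity procedure. No step-down or hierarchical rule appears anywhere. Section 5.0 shows that the cycle-phase comparison is made within the same women: "Study visit 2 will be scheduled in order to coincide with opposite phase from study 1".

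**The concern.** A fixed 0.025 for each comparison ignores what the other comparison shows. On the example means, the estrogen comparison is almost sure to succeed, and the cycle-phase comparison has half the expected difference. Once the first has been rejected, its share of the 5% is no longer needed to protect it. Single-step Bonferroni leaves that share unspent, while Holm passes it on.

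Section 3.0 commits to only five reproductive-age completers as a minimum. In a group that small, the threshold can matter a good deal to whether a 40 um phase difference is declared. At stake is power that could be recovered without recruiting anyone. Error control is not in question.

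**Working it through.** **Inputs.** From Section 10: SD 18 um, sizing difference 40 um, example differences 180 − 100 = 80 um (estrogen) and 240 − 200 = 40 um (phase), five per arm, alpha 0.05/2 = 0.025. Assumed because the documents do not say: two-sided tests, and a within-woman correlation rho between phases, shown over a range.

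**The plan's own figure.** For 40 um, SD 18, 80% power and 0.025 per comparison:
- Normal approximation: 4 per arm.
- Two-sample t, two-sided (noncentral t): 76.0% at n = 5 and 86.6% at n = 6, so 6 per arm.
- Two-sample t, one-sided 0.025: 74.5% at n = 4 and 86.7% at n = 5, so 5 per arm.
- Paired t, two-sided, SD of differences 18: 63.9% at n = 4 and 85.9% at n = 5, so 5.

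The stated five is therefore reproducible under two readings.

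**Estrogen versus placebo at 80 um.** Standard error = 18 × √(2/5) = 11.38. Noncentrality = 80/11.38 = 7.03 on 8 df. The two-sided 0.025 critical value is 2.75. Power = 99.98%.

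**Cycle phase at 40 um, n = 5.** Paired: SD of differences = 18 × √(2(1 − rho)); noncentrality = 40/(SD of differences/√5) on 4 df; critical values 3.50 at 0.025 and 2.78 at 0.05. With the estrogen comparison rejecting 99.98% of the time, Holm power equals power at 0.05 to the accuracy shown.

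| Form | SD of differences | Bonferroni (0.025) | Holm (in effect 0.05) | Gain, points |
|---|---|---|---|---|
| Paired, rho 0 | 25.5 | 57.0% | 74.8% | 17.8 |
| Paired, rho 0.25 | 22.0 | 69.8% | 85.3% | 15.5 |
| Paired, rho 0.5 | 18.0 | 85.9% | 95.3% | 9.4 |
| Paired, rho 0.7 | 13.9 | 97.3% | 99.6% | 2.3 |
| Paired, rho 0.8 | 11.4 | 99.7% | 100.0% | 0.3 |
| Unpaired t-test | – | 76.0% | 86.7% | 10.7 |

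Simulation with 300,000 runs gave Holm gains of 17.7 (rho 0), 9.4 (rho 0.5) and 10.8 (unpaired) points.

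**If the estrogen effect is only the 40 um sizing difference.** The two comparisons use different women, so their p-values are independent, and Holm power for estrogen = P(p ≤ 0.025) + P(0.025 < p ≤ 0.05) × (phase power at 0.025).
- Rho 0: 0.760 + (0.867 − 0.760) × 0.570 = 0.821.
- Rho 0.8: 0.760 + 0.107 × 0.997 = 0.867.

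Estrogen power thus rises from 76% to about 82–87%. Phase power at rho 0 is then 0.570 + 0.178 × 0.760 = 0.705.

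**Familywise error.** With both nulls true, either rule makes a false claim only if the smaller p-value is at most 0.025: 1 − 0.975² = 4.9%. With the estrogen effect real and no phase effect, the only possible false claim is on phase: 2.5% under Bonferroni and 5.0% under Holm (simulated 0.0250 and 0.0497). Both stay within 5%.

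**The case against.** **Bonferroni appears only as a sizing assumption.** It stands in the power paragraph, and the analysis paragraph names ANOVA or Kruskal-Wallis. This is a fair reading. It does not remove the point, because no other multiplicity rule is given. It does mean that a Holm sentence must also name the tests that produce the two p-values.

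**The size of the gain is uncertain.** This stands. A reader might infer a gain of 9 to 18 points throughout. That range covers only correlations from 0 to 0.5, and for repeat measurements in the same women a higher value cannot be excluded. If 0.025 was meant one-sided, the unpaired gain is 7.3 points (86.7% to 94.0%).

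**Near-certain rejection rests on example means and on SD 18.** This also stands. At 80 um, power for estrogen versus placebo at 0.025 is 97.5% with SD 25 and 89.9% with SD 30. At 40 um it is 76%, and the cycle-phase gain on the unpaired form falls to about 8 points.

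**The stricter threshold is a defensible choice.** Bonferroni is valid, the study is preliminary, and Section 2.0 describes the younger women as a positive control. On the example means the randomized comparison gains essentially nothing. This limits how much weight the point should carry, but it gives no reason to prefer the less powerful of two rules with the same familywise guarantee.

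**Conclusion.** The point holds as a loss of efficiency. Single-step Bonferroni is a valid rule, and Holm dominates it at the same 5% familywise error. On the plan's example means with SD 18, five per arm and two-sided tests, the gain in cycle-phase power is about 18 points at rho 0, 16 at 0.25, 9 at 0.5, 2 at 0.7 and near 0 from 0.8. It is 11 points on an unpaired test. If the estrogen effect is only 40 um, the randomized comparison gains too, from 76% to about 82–87%.

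The documents do not support two stronger readings:
- **That Holm brings five per arm to 80% for each comparison.** The two-sample calculation suggests this (about 87% for cycle phase if the estrogen effect is 80 um, or 84% each if both differences are 40 um). But cycle phase is a paired comparison on 4 df, and at rho 0 it reaches only 75%, or 71% if the estrogen effect is 40 um.
- **That five per arm necessarily miss 80% under Bonferroni.** This is so for an unpaired two-sided test (76%). It is not so for a one-sided test (86.7%) or a paired test with SD of differences 18 (85.9%), and the plan does not say which was used.

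**What to change.** In Section 10, state that the two primary OCT comparisons will be tested with the Holm procedure at a two-sided familywise 5%. The smaller p-value is compared with 0.025 and, if it is significant, the larger with 0.05. Name the tests that supply the p-values: a two-sample t-test for estrogen versus placebo, and a paired t-test for follicular versus luteal phase in the same women. Say how these relate to the ANOVA and Kruskal-Wallis text.

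Restate power on that basis. For cycle phase, use the paired form with a stated assumed correlation or SD of differences, preferably over a range such as the one above. Do not claim 80% for each comparison without that condition.

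The cost is a few sentences and a restated power figure, with no added participants, visits or assays. There are two downsides. When the estrogen effect is real, the chance of a false cycle-phase claim rises from 2.5% to 5%, still within the planned familywise 5%. And simultaneous confidence intervals that match Holm are less simple than Bonferroni intervals; unadjusted 95% intervals, labelled as such, can be reported beside the Holm decisions.

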11.0 Ethics and the Protection of Human Subjects

The PI will ensure that this study is conducted in full conformity with applicable regulations and UTMB IRB policies and procedures. Any amendments to the protocol or consent materials will be approved by the IRB before they are placed into use.

Potential candidates will be asked to read and review the approved study consent form. The study clinician will review the consent document with the candidate. Upon reviewing the document, the investigator will explain the research study to the subject and answer any questions that may arise. Potential candidates will have the opportunity to take the consent form home to discuss the study with family members, friends or other providers. Study candidates will sign the informed consent document prior to any procedures being done specifically for the study. Subjects may withdraw consent at any time throughout the course of the trial. A copy of the informed consent document will be given to the subjects for their records. The rights and welfare of the subjects will be protected by emphasizing to them that the quality of their medical care will not be adversely affected if they decline to participate in this study.

Study participants will be informed of any abnormality that may be discovered upon the study ultrasound and referred for further evaluation and testing.

Data and Safety Monitoring Plan

Oversight of internal monitoring of the participants' safety and data quality will be conducted by the PI, along with members of the research team. The PI will assume primary responsibility for monitoring the safety of the study participants. If any safety concerns are identified, then reasonable and appropriate actions to be taken will be discussed with the investigative team.

Data integrity and security is the responsibility of all study personnel and will be carefully monitored by the investigators. All study paperwork will be stored in a locked file cabinet accessible only to designated research staff. Electronic data (i.e., computer files) will be created and accessed solely by project personnel and be password protected to guard against loss.

Study investigators are instructed to report adverse events to the PI and study coordinator. All serious adverse events and unanticipated problems will be reported to the UTMB IRB immediately by telephone and by written report within 24 hours of receipt of notice. Non-serious events requiring reporting to the IRB will be done in a prompt manner, within the 10-working day window. The research team members will review adverse events, SAEs and unanticipated problems as they are arise and make modifications to the protocol and consent form as warranted.

Privacy/Confidentiality Issues

Subject confidentiality is strictly held in trust by the participating investigators, their staff, and any sponsor. This confidentiality is extended to cover testing of biological samples in addition to the clinical information relating to participating subjects. No information concerning the study or the data will be released to any unauthorized third party without prior written approval of the Principal investigator.

Individuals authorized to view study records are identified to the study subject on the informed consent. Study records may also be made available for internal compliance reviews and quality assurance representatives.

In accordance with the Food and Drug Administration Amendment Act of 2007 (FDAAA) and The International Committee of Medical Journal Editors (ICMJE) member journals trials-registration policy as a condition for publication, this study will be registered in the public trials registry ClinicalTrials.gov, which is sponsored by the National Library of Medicine. Results will be published to clinicalTrial.gov when available but will not identify individual subjects.

